### 9.2.2.2. Pharmacokinetics Analyses

#### Pharmacokinetic Parameters

To assess the pharmacokinetics of PF-06647263 (ADC), total antibody and unconjugated payload, the PK parameters detailed in [Section 7.3](#) will be listed and summarized for subjects in the PK analysis set (as defined in [Section 6.4](#)). Missing values will be handled as detailed in [Section 8](#). Each PK parameter will be summarized by dose and cycle and will include the set of summary statistics as specified in the table below:

Parameter	Summary statistics
AUC last , AUC ∞ , AUC T0 , C max , CL, V ss , and R ac	N, arithmetic mean, median, cv%, standard deviation, minimum, maximum, geometric mean
t 1/2	N, arithmetic mean, median, cv%, standard deviation, minimum, maximum
T max	N, median, minimum, maximum

There will be 1 summary table presenting all PK parameters. This will include data from all cohorts and will be summarized by dose group and cycle.

To assess the relationship between the PK parameters and dose, dose normalized  $AUC_{\infty}$ ,  $AUC_{last}$ ,  $AUC_{t_1}$ , and  $C_{max}$  will be plotted against dose (using a logarithmic scale), and will include individual subject values and the geometric means for each dose. Geometric means will have a different symbol than the individual values. The values will be dose normalized (to a 1 mg/kg dose) by dividing the individual values and raw geometric means by dose. A footnote will be added to the plots to indicate that geometric means are presented are presented on the plot.

### Pharmacokinetic Concentrations

To assess the PK profile of PF-06647263 (ADC), total antibody and unconjugated payload, PK concentrations will be listed, summarized and plotted for subjects in the PK analysis set (as defined in [Section 6.4](#)), where missing and BLQ values will be handled as detailed in [Section 8.3](#).

Presentations for PF-06647263 (ADC), total antibody and unconjugated payload will include:

- a listing of all concentrations sorted by dose, subject id, day and nominal time post dose. The listing of concentrations will include the actual times. Deviations from the nominal time will be given in a separate listing.
- a summary of concentrations by dose, day and nominal time post dose, where the set of statistics will include n, mean, median, standard deviation, coefficient of variation (cv) and the number of concentrations above the lower limit of quantification.
- a plot of mean concentrations against nominal time postdose by dose (based on the summary of concentrations by dose and time postdose), preferably with all doses also on the same graph.
- a plot of median concentrations against nominal time postdose by dose (based on the summary of concentrations by dose and time postdose), preferably with all doses also on the same graph.
- a log-linear plot of mean concentrations against nominal time postdose by dose (on the same plot), preferably with all doses also on the same graph.
- a log-linear plot of median concentrations against nominal time postdose by dose (on the same plot), preferably with all doses also on the same graph.
- plots (linear and log scale) of individual concentrations against actual time postdose.

The length of time used for the x-axes of these plots will be decided on review of the data, and will depend on how long PK concentration is quantifiable in the matrix.

In addition to the above, a median plot (linear and log scale) of the predose concentrations at each cycle against day will be provided for each dose, on the same plot, in order to assess the attainment of steady-state. Individual subject profiles will also be plotted.

For summary statistics and mean/median plots by sampling time, the nominal PK sampling time will be used, for individual subject plots by time, the actual PK sampling time will be used.

### **Population Pharmacokinetic Analysis or PK/PD Modeling**

Pharmacokinetic and pharmacodynamic data from this study may be analyzed using compartmental or mixed-effect modeling approaches and may also be pooled with other study results. PK/PD modeling may be attempted to investigate any causal relationship between PF-06647263 exposure and biomarkers or significant safety endpoints. The results of these analyses, if performed, may be reported separately.

CCI [REDACTED]

[REDACTED]

[REDACTED]

[REDACTED]

#### **9.2.3. Safety Analyses**

##### **Adverse Events**

Adverse Events (AEs) will be graded by the investigator according to the CTCAE version 4.0 and coded using the MedDRA. The focus of AE summaries will be on Treatment Emergent Adverse Events, those with initial onset or increasing in severity after the first dose of study medication. The number and percentage of patients who experienced any AE, serious AE (SAE), treatment related AE, and treatment related SAE will be summarized according to worst toxicity grades. The summaries will present AEs both on the entire study period and by cycle (Cycle 1 and Cycles beyond 1). The Safety Analysis Set will be used.

##### **Laboratory Tests Abnormalities**

The number and percentage of patients who experienced laboratory test abnormalities will be summarized according to worst toxicity grade observed for each laboratory test. The analyses will summarize laboratory tests both in the entire study period and by cycle (Cycle 1 and Cycles beyond 1). Shift tables will be provided to examine the distribution of laboratory abnormalities. The Safety Analysis Set will be used.

For laboratory tests without CTC grade definitions, results will be categorized as normal, abnormal high/low or not done.

**Other Variables: Anti-PF-06647263 antibody**

For anti-PF-06647263 antibody, a listing, sorted by subject and study day, of the result of anti-PF-06647263 antibody screening (positive/negative [ $<1$ :negative]), the specificity, and titer will be listed. Summary counts of the patients, who are positive for the antibody, will be derived by study treatment and visit for the safety population. No summary statistics other than those cited above, will be generated.

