## Secondary Objectives

- To evaluate the overall safety profile at the RP2D;
- To characterize the single and multiple dose PK of PF-06647263, total antibody, and unconjugated payload;
- To evaluate the immunogenicity of PF-06647263;
- To document preliminary evidence of anti-tumor activity based on progression free survival (PFS) and overall survival (OS).

CCI [REDACTED]

[REDACTED]

[REDACTED]

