### Secondary Endpoints (Parts 1 and 2)

- Adverse Events as characterized by type, frequency, severity (as graded by NCI CTCAE v.4.03), timing, seriousness and relationship to study therapy;
- Laboratory abnormalities as characterized by type, frequency, severity (as graded by NCI CTCAE v.4.03) and timing;
- Vital Sign abnormalities;
- Systemic PK exposure of PF-06647263, total antibody, and unconjugated payload will be determined with validated methods. Standard noncompartmental PK parameters will be determined from the respective concentration-time data;

- Immunogenicity of PF-06647263; Human serum ADA (anti-PF-06647263 antibody) samples will be analyzed for the presence or absence of anti-PF-06647263 antibodies, following a tiered approach using screening, confirmation and titer/quantitation;
- Objective tumor response, as assessed using RECIST version 1.1 by calculating the Overall Response Rate (ORR), Clinical Benefit Response Rate (CBRR), Progression Free Survival (PFS), and Overall Survival (OS)-Part 2 only.

CCI [REDACTED]

[REDACTED]

[REDACTED]

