### **5. SAMPLE SIZE DETERMINATION**

Similar to the conventional 3+3 design, the exact sample size of the mTPI design in Part 1 cannot be pre-specified in advance because it is a dynamic feature of the design. The minimum sample size after which the Part 1 can be stopped and MTD declared is 9. If two dose regimens are evaluated, the maximum sample size would be 70 patients.

As for the number of subjects treated at each dose, it is expected that the typical number will be 2-4 subjects for the doses actually studied. For the dose declared as MTD at the end of trial, this number will be at least 9. However, since variable cohort size is allowed, the actual number of subjects treated at each dose will vary from 2 to 12. For example, N=12 is achieved if 4 additional patients are enrolled in a cohort of n=8.

The sample size in Part 2 is based on clinical considerations, rather than statistical justification. It will include 30 subjects in two cohorts of tumor types of interest (ie, TNBC and OVCA) to confirm the safety and tolerability of the recommended dose based on Part 1 and to assess preliminary anti-tumor activity.

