#### **7.2.8. Immunogenicity**

Anti-PF-06647263 antibody data will be collected at baseline and post randomization according to the protocol.

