#### **Analyses of Binary Endpoint**

The rates of binary endpoints will be provided along with the corresponding 2-sided 95% confidence intervals using an exact method.

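### The ADA summary is restricted to positive counts by visit, so the number of patients who developed or boosted antibody on treatment is not tabulated

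*SAP*

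**What the plan says.** SAP section 2.4 gives the same secondary objective for Part 1 and Part 2: "To evaluate the immunogenicity of PF-06647263". The matching secondary endpoint is binary with a titer attached: "samples will be analyzed for the presence or absence of anti-PF-06647263 antibodies, following a tiered approach using screening, confirmation and titer/quantitation".

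Section 7.2.8 fixes the sampling: "Anti-PF-06647263 antibody data will be collected at baseline and post randomization according to the protocol". The study is not randomized, so this is read here as baseline and post-dose samples.

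Section 9.2.3, under the heading for anti-PF-06647263 antibody, plans two outputs:

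- a listing ordered by patient and day, in which the screening result, "the specificity, and titer will be listed";
- one summary: "Summary counts of the patients, who are positive for the antibody, will be derived by study treatment and visit for the safety population".

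The paragraph then ends: "No summary statistics other than those cited above, will be generated".

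Section 9.1 sets the general rule for binary data: "The rates of binary endpoints will be provided along with the corresponding 2-sided 95% confidence intervals using an exact method".

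**The concern.** An immunogenicity evaluation normally has to say how many patients mounted or increased an antibody response after exposure. That is a within-patient comparison of later samples with baseline. The planned table holds only the total number of positives at each visit, so it cannot show whether a patient positive later was negative before dosing, or whether the positives at two visits are the same patients. A titer rise in a patient already positive at baseline does not appear in a positive/negative count at all.

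This is an express restriction, not a detail left open, because the closing sentence bars the missing summary. What is at stake is a prespecified estimate for a secondary objective. Without one, any incidence figure in the study report would be classified by hand after the data are seen, under a rule chosen at that point.

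**Working it through.** The SAP states no ADA rate or precision, so there is no figure to reproduce. The check has three steps.

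**1. What the planned outputs contain**

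| Quantity | By-visit counts | Listing |
|---|---|---|
| Positives at each visit | Yes | By hand |
| Patients ever positive after dosing | No | By hand |
| Baseline negative, later positive | No | By hand |
| Titer rise over a positive baseline | No | By hand, with no threshold fixed |
| Rate with exact interval | No, and barred | No |

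**2. How far the by-visit counts leave incidence open**

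Let *N* patients be sampled at every visit, with *b* positive at baseline and *c₁, c₂, c₃* positive at three later visits. Count a patient as newly positive if negative at baseline and positive at least once afterwards. From the counts alone:

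- lower bound = max(0, largest *c* − *b*)
- upper bound = min(*N* − *b*, *c₁* + *c₂* + *c₃*)

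All counts below are assumed. Only the sizes come from the SAP: section 5 states "It will include 30 subjects in two cohorts of tumor types of interest", and section 2.3 gives 15 per tumor type.

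| N | b | Later visits | Lower | Upper | Share of N |
|---|---|---|---|---|---|
| 15 | 2 | 2, 2, 2 | max(0, 2 − 2) = 0 | min(13, 6) = 6 | 0% to 40% |
| 30 | 3 | 3, 3, 3 | max(0, 3 − 3) = 0 | min(27, 9) = 9 | 0% to 30% |
| 30 | 0 | 3, 3, 3 | max(0, 3 − 0) = 3 | min(30, 9) = 9 | 10% to 30% |

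Two patterns show why the first row is so wide. If the same two patients are positive throughout, nobody is newly positive. If two patients are positive at baseline only and a different pair is positive at each later visit, six are. Both patterns print the same row of 2, 2, 2, 2.

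**3. What a per-patient rate would give**

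Exact (Clopper-Pearson) 95% intervals, the kind section 9.1 calls for:

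- 0 of 30: upper limit 1 − 0.025^(1/30) = 11.6%, so 0% to 11.6%
- 3 of 30: 2.1% to 26.5%
- 0 of 15: upper limit 1 − 0.025^(1/15) = 21.8%, so 0% to 21.8%

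These intervals are wide, but they are usable descriptive statements. The planned table supports none of them.

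**The case against.** The strongest reply is that the listing already holds the information. Section 5 expects 2 to 12 patients at a dose and 30 in Part 2. At that size a reader can follow each patient from baseline and count conversions and titer rises directly, which removes the ambiguity in step 2. This stands. A reader might infer that the immunogenicity objective cannot be answered from the planned output, and the listing shows that this goes too far. What remains is that a listing is not a prespecified estimate, and no rule for a conversion or a meaningful titer rise is fixed.

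Three other inferences are not supported by the text:

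- **Percentages that fall with dropout.** A reader might take the safety population as the denominator of visit percentages. Section 9.2.3 plans ADA counts only, whereas for adverse events and laboratory tests it asks for percentages as well. Naming the safety population identifies the analysis set. It does not state a denominator.
- **Pre-existing antibody hidden in the results.** Baseline is sampled and counts are by visit, so baseline most likely has its own row. Only the within-patient link is missing.
- **Treatment-emergent ADA as the stated objective.** The objective says only immunogenicity. In the text available, treatment-emergent is defined for adverse events, not for antibody. It is used here as the quantity that best answers the objective.

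It can also be said that section 9.1 is general and names no ADA endpoint, so the ADA paragraph might be meant as an exception. That is possible, but the SAP does not say so, and presence or absence of antibody is a binary endpoint. Finally, the upper bounds in step 2 are extremes: they require every later positive result to come from a different patient.

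**Conclusion.** The point holds in limited form. Followed as written, the SAP produces no per-patient ADA incidence and no tabulated link between baseline and later results, and its closing sentence prevents one from being added. That conflicts with the general rule for binary endpoints in section 9.1. The data needed are planned for collection, and the cases could be counted by hand from the listing, so what is lost is a prespecified, tabulated estimate and not the information itself.

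The weight is minor. This is a single-arm, descriptive Phase 1 study with no hypothesis tests, and no dose decision or analysis set in the visible text depends on ADA. The 0% to 40% range illustrates the ambiguity under assumed counts and complete sampling. It is not a forecast.

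**What to change.** Replace the last sentence of the ADA paragraph in section 9.2.3 with a per-patient summary:

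- **Measure:** number and percentage of patients with treatment-emergent ADA, with an exact 95% confidence interval as in section 9.1.
- **Definition:** baseline negative with any post-dose positive, or a titer rise over a positive baseline of a size fixed before analysis.
- **Denominator:** patients with a baseline sample and at least one post-dose sample.
- **Grouping:** by regimen and dose, and by tumor cohort in Part 2.
- **Alongside the by-visit counts:** baseline prevalence, and the number of patients sampled at each visit.

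Keep the listing and the by-visit counts. The cost is one extra table and a short definition. No new samples, visits or patients are needed.

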**9.2.4. Standard Analyses****Study Conduct and Patient Disposition**

An accounting of the study patients will be tabulated. The subject evaluation groups will be listed. The Full Analysis Set will be used.

Subject discontinuation from treatment and study will be tabulated and listed separately with their reason for discontinuation. The Safety Analysis Set will be used.

**Baseline Characteristics**

Baseline characteristics such as demographics, prior medication, medical history, ECOG performance status, and primary diagnosis will be tabulated and listed. For ECOG performance status a shift table (worst post-baseline vs baseline may be produced). The Safety Analysis Set will be used.

**Treatment Administration/Compliance**

Listings and tables by dose level will be provided. Cycle length is 21 days. Day 1 of a cycle is the first date of dose within that cycle. The safety analysis set will be used.

Dose modifications may occur in the following ways:

- Cycle delay—Day 1 of current cycle starts later than 21 days from Day 1 of the previous cycle (only applies to cycle 2 and above);
- Dose reduction—A decrease in the administered total daily dose (non-zero) compared to the planned total daily dose upon enrollment. If in the CRF the prescribed dose unit is mg/kg, but the actual dose is in mg the actual dose mg/kg should be calculated considering the body weight of the patient at that visit.

Intra-patient dose escalation is not allowed in this study. The following will be summarized by subject for each dose level:

- Number of subjects per dose level
- Median and range of number of cycles started per subject
- Number (%) of subjects starting a cycle (1, 2, 3...)

- Number (%) of subjects with cycle delays
- Number (%) of dose interruptions (include both known and unknown dates)
- Number (%) of subjects with dose reductions
- Number (%) of each reason (AE vs. Other) for cycle delays, dose interruptions and dose reductions
- Time on treatment (median, range)

The following will be summarized by cycle received for each dose level:

- Total number of cycles started
- Number of cycles started per subject (median, range)
- Number of cycles before 1st delay (median, range)
- Number of cycles before 1st reduction (median, range)
- Number of cycles before 1st interruption (median, range)

The following will be summarized for cumulative dose by dose level and cycle:

- Summary statistics (mean, median, standard deviation and range) of cumulative dose and percent of starting dose (compared to Day 1 dose of each cycle)

Listings by subject (ordered by dose level): start date and stop date of each dosing period within each cycle (including records with 0 mg), administered total daily dose for each period, any missed doses with unknown dates (Y/N), number of missed doses with unknown dates, reason for any dosing changes.

Listings by subject and each cycle (ordered by dose level): cycle length, total planned dose, administered total dose, percentage of planned dose, dose delay (yes/no), dose reduction (yes/no), and dose interruption (yes/no).

### **Prior, Concomitant, and Further Therapies**

Prior, concomitant, and further therapies (drug and non-drug treatments) will be coded by the World Health Organization (WHO) medical dictionary. Listings of prior, concomitant, and further therapies will be provided separately.

## 11. APPENDICES

### 11.1. APPENDIX 1: CATEGORICAL CLASSES FOR ECG AND VITAL SIGNS

#### Categories for QTcB and QTcF

QTcB/QTcF (ms)	max. $\leq$ 450	450 $<$ max. $\leq$ 480	480 $<$ max. $\leq$ 500	max. $>$ 500
QTcB/QTcF (ms) increase from baseline	max. $<$ 30	30 $\leq$ max. $<$ 60	max. $\geq$ 60	

#### Categories for PR and QRS

PR (ms)	max $\geq$ 300	
PR (ms) increase from baseline	Baseline $>$ 200 and max. $\geq$ 25% increase	Baseline $\leq$ 200 and max. $\geq$ 50% increase
QRS (ms)	max $\geq$ 200	
QRS (ms) increase from baseline	Baseline $>$ 100 and max. $\geq$ 25% increase	Baseline $\leq$ 100 and max. $\geq$ 50% increase

#### Categories for Vital Signs

Systolic BP (mm Hg)	min. $<$ 90	
Systolic BP (mm Hg) change from baseline	max. decrease $\geq$ 30	max. increase $\geq$ 30
Diastolic BP (mm Hg)	min. $<$ 50	
Diastolic BP (mm Hg) change from baseline	max. decrease $\geq$ 20	max. increase $\geq$ 20
Supine pulse rate (bpm)	min. $<$ 40	max. $>$ 120

Measurements that fulfil these criteria are to be listed in the study report.

## 11.2. APPENDIX 2: RECIST 1.1 TUMOR ASSESSMENT CRITERIA

At baseline, individual tumor lesions will be categorized by the investigator as either measurable or not, according to the criteria summarized below:

### **Measurable Lesions**

Lesions that can be accurately measured in at least one dimension (longest diameter in the plane of measurement is to be recorded) with a minimum size of:

- 10 mm for lesions other than lymph nodes and assessed by CT scan (CT scan slice thickness no greater than 5 mm)
- 10 mm for lesions assessed clinically by caliper measurement (lesions which cannot be accurately measured with calipers should be recorded as non-measurable).
- 20 mm for lesions assessed by chest X-ray.
- 15 mm in short axis for lymph nodes when assessed by CT scan (CT scan slice thickness recommended to be no greater than 5 mm).

### **Non-measurable Lesions**

Non-measurable lesions include small lesions (longest diameter <10 mm or pathological lymph nodes with a  $\geq 10$  but  $< 15$  mm short axis) as well as truly non-measurable lesions. Truly non-measurable lesions include: leptomeningeal disease, ascites, pleural or pericardial effusion, inflammatory breast disease, lymphangitic involvement of skin or lung, abdominal masses identified by physical exam and not measurable by reproducible imaging techniques.

Nodes that have a short axis  $<10$  mm are considered non-pathological and should not be recorded or followed.

### **Special Considerations Regarding Specific Lesions**

#### **Bone lesions:**

- Bone scan, PET scan or plain films are not considered adequate imaging techniques to measure bone lesions. However, these techniques can be used to confirm the presence or disappearance of bone lesions.
- Lytic bone lesions or mixed lytic-blastic lesions, with identifiable soft tissue components, that can be evaluated by cross sectional imaging techniques such as CT or MRI can be considered as measurable lesions if the soft tissue component meets the definition of measurability described above.

- Blastic bone lesions are non-measurable.

**Cystic lesions:**

- Lesions that meet the criteria for radiographically defined simple cysts should not be considered as malignant lesions (neither measurable nor non-measurable) since they are, by definition, simple cysts.
- 'Cystic lesions' thought to represent cystic metastases can be considered as measurable lesions, if they meet the definition of measurability described above. However, if non-cystic lesions are present in the same patient, these are preferred for selection as target lesions.

**Lesions with prior local treatment:**

- Tumor lesions situated in a previously irradiated area, or in an area subjected to other loco-regional therapy, are usually not considered measurable unless there has been demonstrated progression in the lesion.

